### **Secondary Outcome Measures:**

- Eye movement tracking: movements to first saccades. We will be analyzing change from baseline eye movement tracking results at 8 weeks.
- Female Sexual Function Index: change from baseline to final score at 8 weeks.
- UCLA Loneliness Scale: change from baseline to final score at 8 weeks.
- Life Satisfaction Scale: change from baseline to final score at 8 weeks.
- Body Dysmorphic Disorder Questionnaire: change in answers from baseline to final visit at 8 weeks.
- Hamilton Anxiety and Depression Scale: change from baseline to final score at 8 weeks.
- Rosenberg Self-Esteem Scale: change from baseline to final score at 8 weeks.
- Hostility Measure: change from baseline to final score at 8 weeks.
- Female Sexual Distress Scale-Revised: change from baseline to final score at 8 weeks.
- IOS Scale with Partner: change in answers from baseline to final answers at 8 weeks.
- Body image measure: change in baseline to final score at 8 weeks.
- Sexual Desire Inventory: change in baseline to final score at 8 weeks.
- Marital Satisfaction Scale: change in baseline to final score at 8 weeks.

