**Statistical Hypotheses:**

a. The research questions of this double-blind randomized study are: (a) to determine the pre-post change in the Flibanserin group vs. Placebo group in women with hypoactive sexual desire disorder (HSDD), (b) to compare the effect is Flibanserin (vs. placebo) on behavioral and brain changes between pre-menopausal women and postmenopausal women, (c) to investigate the extent to which post-Flibanserin's regional brain activations (compared to pre-Flibanserin's regional brain activations) are associated with changes in symptoms and behavior (as measured with self-report measures of sexual desire and/or eye-tracking movements), and (d) to investigate the extent to which Flibanserin normalizes brain activity in women with HSDD compared to matched healthy controls. The statistical hypotheses include the following:

i. Demographics: Statistical analyses for demographic and self-report measures will be computed using SPSS software. Prior to inferential analyses, descriptive statistics, including distributions, means, standard deviations, skewness, and kurtosis will be generated. Data will also be examined for the pattern and mechanism of missing data. Continuous data will be tested for normality and homogeneity of variance. Potential differences between the treatment and placebo groups in terms of demographic and behavioral measures will be explored using multivariate analysis of variance (MANOVA) or appropriate non-parametric tests as appropriate. Similar analyses will be performed to detect potential differences between the pre-menopausal subjects and the post-menopausal subjects. The overall significance level for these analyses will be at 5%, and effect sizes and confidence intervals will also be performed to test hypotheses about correlations.

ii. Behavioral data: Statistical analyses will be computed using SPSS software. Reaction times and performance data (ratings) will be screened. Prior to inferential analyses, descriptive statistics, including distributions, means, standard deviations, skewness, and kurtosis will be generated. Data will also be examined for the pattern

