and mechanism of missing data. A 2 (Treatment Type: Addyi or Placebo) x 2 (Group Type: pre- or post-menopausal) X 2 (type of stimuli: desired, nondesired) x 3 time (Visit 1, Visit 2, Visit 3) repeated-measures ANOVA will be performed on the reaction times and ratings to assess for main effects and interaction effects. P values, confidence interval, and effect sizes will be reported.

iii. Eye-tracking Data: A similar ANOVA will be performed for the following dependent variables: onset to first fixation and duration of fixation. As in our 2014's paper (Bolmont, Cacioppo, & Cacioppo), we will also analyzed include the subjects' visual area of interest (face vs. body) as a within-subject factors in our ANOVA.

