iii. Electrophysiological Data: EEG data will be analyzed using an established Matlab toolbox, CENA (The Chicago Electrical Neuroimaging Analytics). Standard statistical analyses will be performed using SPSS. Compared to fMRI, which has a very low temporal resolution, high-density EEG/ERP has a very high temporal resolution ([name] & Bianchi-Demicheli, 2008). When combined with brain source localization algorithms, high-density EEG-ERP is called electrical neuroimaging. Electrical neuroimaging can identify dynamical patterns of communication between brain regions that contrast analyses, such as fMRI, may not detect. This proposal takes advantage of electrical neuroimaging and a new suite of tools (i.e., the Chicago Electrical Neuroimaging Analytics, CENA), that [name] developed and validated recently for segmenting high-density electrical brain activity (Cacioppo et al., 2014, 2015). Compared to the standard waveform analysis of event-related potentials (ERP) components that provide local information about amplitude and latency of the brain electric signal collected from one electrode in response to a stimulus, CENA provides general information about the stable momentary configuration of the global scalp electric potential over a high-density multi-channel electrode array. This approach provides information about the temporal sequence of discrete information processing operations evoked by the presentation of a stimulus within the context of a particular experimental task. That temporal sequence of information processing includes a series of stable brain microstates, each of which is characterized by specific cognitive computations and a relatively stable spatial distribution of brain activity. Combined with brain source localization algorithms, this method can then provide a video-clip of the

potential brain sources that sustain every electrical brain state recorded from the surface of the scalp –without having to perform an fMRI scan (see attached example). The brain microstate approach complements the traditional approach of ERP peaks and troughs at specific electrode positions, but with more comprehensive analyses of time-varying activity across the entire scalp (Cacioppo et al., 2014, 2015).

A significant and clinically meaningful change from baseline for each subject pre- and post-treatment with flibanserin is as follows:

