Median effective doses of flibanserin on increase in SD level will demonstrate at least a medium effect size (e.g., Cohen's  $d > 0.48$ ) relative to placebo (PBO); and at least a medium effect size (Cohen's  $d > 0.48$ ) between flibanserin and PBO conditions in SD levels; and relationship between change in SD self-report levels and change in behavioral responses (reaction times) during SD paradigm in flibanserin (vs PBO) is of at least a medium effect size ( $r > 0.48$ ); or relationship between change in flibanserin and change in electrophysiological responses during SD paradigms in flibanserin (vs. PBO) is of at least a medium effect size ( $r > 0.48$ ); Relationship between change in Flibanserin and change in eye movement responses during SD paradigms in Flibanserin(vs. PBO) is of at least a medium effect size ( $r > 0.48$ ). There will be no adverse events of more than mild severity which are rated as possibly, probably, or definitely related to acute, oral administration of flibanserin to a greater extent than PBO in HSDD participants.

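### The criterion for a clinically meaningful change cannot be applied: one of its variables is undefined and its and/or chain has no brackets

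*Combined protocol and SAP*

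**What the plan says.** Under Statistical Hypotheses in section 11, the electrophysiology item ends with this lead-in: "A significant and clinically meaningful change from baseline for each subject pre- and post-treatment with flibanserin is as follows". The conditions that follow are (SD is taken to mean sexual desire):

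- two conditions on desire, each a Cohen's d above 0.48 against placebo, joined by 'and';
- after another 'and', a correlation above 0.48 between change in self-reported desire and change in reaction time;
- after 'or', a correlation above 0.48 for the "relationship between change in flibanserin and change in electrophysiological responses during SD paradigms in flibanserin (vs. PBO");
- with a capital letter and no connective, "Relationship between change in Flibanserin and change in eye movement responses during SD paradigms", again with r above 0.48;
- a closing sentence on adverse events.

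Related text elsewhere:

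- Research question (a) is "to determine the pre-post change in the Flibanserin group vs. Placebo group". Question (c) asks how far regional brain activations "are associated with changes in symptoms and behavior (as measured with self-report measures of sexual desire and/or eye-tracking movements").
- The secondary outcomes include "Sexual Desire Inventory: change in baseline to final score at 8 weeks" and "Eye movement tracking: movements to first saccades".
- For behavioural data, a "repeated-measures ANOVA will be performed on the reaction times and ratings to assess for main effects and interaction effects". The eye-tracking item applies a similar ANOVA to two other measures, time to first fixation and fixation duration.
- Section 5 assigns one fixed regimen, 60 women per arm.

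**The concern.** This is the only place in section 11 that puts numbers on a meaningful change. Two features stop anyone from applying it. The EEG and eye-movement clauses correlate outcome change with a quantity that has no definition. And the connectives do not say whether the EEG correlation is an alternative to the desire effect, or an alternative only to the reaction-time correlation. The eye-movement clause has no stated role at all.

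The same results could therefore be reported as meeting or missing the criterion, depending on a reading chosen after the data are seen. On one reading, a desire-EEG correlation, which can exist without any drug effect, would be enough.

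**Working it through.** **Inputs.** From the plan: cut-offs d > 0.48 and r > 0.48, 60 per arm, one regimen. The criterion contains no computed figure to reproduce. The 95% power in section 10 is tied to no outcome and is not used here.

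**1. The undefined variable.** If the change in flibanserin means dose, it is constant within an arm assigned one regimen, and a correlation with a constant does not exist. Change in self-reported desire is probably meant, by parallel with the reaction-time clause and question (c), but the text does not say so. Even then the score is open: the Sexual Desire Inventory and the task ratings are both candidates.

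**2. The brackets.** Count the two d conditions once and set the eye clause aside (1 = met):

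| d | RT | EEG | (d and RT) or EEG | d and (RT or EEG) |
|---|---|---|---|---|
| 0 | 0 | 0 | 0 | 0 |
| 0 | 1 | 0 | 0 | 0 |
| 0 | 0 | 1 | **1** | **0** |
| 0 | 1 | 1 | **1** | **0** |
| 1 | 0 | 0 | 0 | 0 |
| 1 | 1 | 0 | 1 | 1 |
| 1 | 0 | 1 | 1 | 1 |
| 1 | 1 | 1 | 1 | 1 |

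They disagree in 2 of 8 patterns, both with d failing and EEG passing. Counting the two d conditions separately gives 3 × 2 = 6 of 16.

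Now let the eye clause be outside the rule, required, or an alternative. Two groupings times three roles make six readings. Over the 16 patterns of (d, RT, EEG, eye), all six agree on not met in 0000, 0100 and 1000, and on met in 1011, 1101 and 1111. They disagree in the other 10.

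**3. No drug effect on desire, r within the flibanserin arm.** Cut-offs are applied to point estimates.

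- Desire: t = 0.48/√(2/60) = 2.63 on 118 df, so P(observed d > 0.48) = 0.0049. Any reading that requires d passes at most about 0.5% of trials.
- EEG, true r 0.5, Fisher's z with its usual bias term: (atanh 0.48 − atanh 0.5 − 0.5/118) × √57 = (0.5230 − 0.5493 − 0.0042) × 7.55 = −0.23, so P(observed r > 0.48) = 0.59. Simulation (200,000 draws) gives 0.593, and 0.055, 0.234 and 0.908 at true r 0.3, 0.4 and 0.6.
- Whole rule at true r 0.5, simulated: (d and RT) or EEG passes 0.590; d and (RT or EEG) passes 0.003.

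**4. r as a between-arm difference, true r equal in both arms.** The standard error of the difference is about √2 × (1 − r²)/√59. At r = 0.3 this is 0.168, and 0.48/0.168 = 2.87, so P is about 0.002. At r = 0.5 it is 0.138, and 0.48/0.138 = 3.48, so P is below 0.001. Simulation gives 0.0021 and 0.0004. Bracketing then hardly matters, because the r clauses almost never pass.

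**5. Pass rates when the drug works, r within arm.** Simulated, 40,000 trials, 60 per arm. True d and r are assumptions. 'Linked through desire' means the three responses correlate with one another only as r².

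| True d, r | Responses | Eye clause outside: d and (RT or EEG) v (d and RT) or EEG | Range over all six readings |
|---|---|---|---|
| 0.60, 0.50 | linked through desire | 60% v 76% | 37%–89% |
| 0.60, 0.50 | correlated 0.8 | 51% v 67% | 39%–74% |
| 0.60, 0.30 | linked through desire | 8% v 9% | 0.5%–15% |
| 0.80, 0.70 | linked through desire | not tabulated | 95%–100% |

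**6. The primary EEG analysis, a separate matter.** Section 4 lists two stimulus comparisons (desired against non-desired; desired against checkerboard) and three features (amplitude, latency, topography): 2 × 3 = 6 combinations before any component or time window is chosen. Section 11 describes microstate segmentation and source localisation for EEG and names the toolbox and SPSS, but no test. The ANOVA is assigned to reaction times and ratings and extended to eye tracking. Its stimulus factor has no checkerboard level.

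**The case against.** The paragraph sits under hypotheses and is worded as a prediction. Nothing in the plan ties a stopping decision or the primary conclusion to it. That is fair: a reader might infer that it is the trial's success rule, and the documents do not say so. But its lead-in presents it as the definition of a meaningful change, and a benchmark with an undefined input and undetermined logic cannot be used as a benchmark either.

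Three stronger readings are tempting and should be resisted.

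- *The criterion can be met with no drug effect.* This needs r read within the flibanserin arm, which gives the placebo comparison written into each r clause no role. On the between-arm reading with equal true r, the result in step 4 applies instead.
- *The and/or chain alone moves the pass rate from 37% to 89%.* Those extremes need the eye clause to be required or an alternative. With that clause outside the rule, which its punctuation allows, the gap is 60% v 76%.
- *The primary outcome has no contrast.* Section 4 names two stimulus contrasts and the 8-week change, and question (a) names the arm comparison. What is missing is a test and a choice among those listed.

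Other points are minor: no sign is given for r, estimate or confidence limit is not stated, and the per-subject lead-in can be read as referring to the individual change scores behind d and r.

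**Conclusion.** The concern holds. As written, the criterion cannot be computed, and its two natural groupings give opposite answers whenever the desire effect misses 0.48 and the EEG correlation exceeds it. The pattern counts (2 of 8; 10 of 16 with the eye clause) rest on the punctuation alone.

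The pass rates are illustrations. They assume normally distributed change scores, 60 per arm, equal correlations in both arms, cut-offs on point estimates and, except in step 4, r within the flibanserin arm. On those terms the choice matters most when the effects lie near the cut-offs or the desire effect is small, and hardly at all at d 0.80, r 0.70.

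The unchosen primary EEG test, contrast and feature is a real but lesser item. Repairing this paragraph would not resolve it, because the EEG clause serves association question (c), not treatment comparison (a). Sections 7 and 19 were not in the text reviewed; section 11 was.

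**What to change.** Before unblinding:

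1. Replace the change-in-flibanserin term with change from baseline to week 8 in one named desire score, and name the eye-movement measure that enters its correlation.
2. State the criterion at group level as the between-arm d on that desire score. Report the reaction-time, EEG and eye-movement correlations by arm and as between-arm differences, each with a 95% CI, as supportive estimates. If the sponsor prefers a compound rule, write it with full brackets, give the eye clause a role, and say whether r is within arm or a difference.
3. Reconcile the references in this paragraph to median effective doses and to acute administration with the single 8-week regimen in section 5.
4. As its own item, name the primary EEG test: the flibanserin-placebo difference in baseline-to-week-8 change for one pre-chosen stimulus contrast and one summary. The summary may be a whole-scalp or microstate measure, in keeping with the planned approach. The other contrast and features become secondary under a stated multiplicity control.

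No new data are needed. The cost is a rewritten criterion, a short EEG analysis specification, and commitment: the sponsor must settle on one desire score and one EEG summary, and the remaining EEG features lose primary status.

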Subjects will be recruited via Flyers posted on Campus and/or in Obstetrics and Gynecology practices and/or via ads posted on Craigslist by research coordinator, [name]. From these ads, interested individuals will be asked to go on Survey Monkey (<https://www.surveymonkey.com/r/HPENlabresearch>) and complete a survey that will help us determine whether they meet our selection criteria or email [name] at [[contact]](mailto:[contact]) or call the research team. Research coordinator will then contact individuals who may meet selection criteria. She and [name] and/or [name] will meet with them and give them the informed consent to read and go through it with the subjects. Upon receipt of a signed informed consent, participants will meet with [name] or [name] who will diagnose them with HSDD. If the subject does not have HSDD, she is not eligible to participate in the study. Subjects with a confirmed diagnosis of HSDD by [name] or [name] will then be randomly assigned by the UChicago Pharmacy/Investigational Drug Service to either Addyi (100 mg once daily at bedtime for 8 weeks, n = 60 subjects) or placebo (100 mg once daily at bedtime for 8 weeks, n = 60 subjects). The research question of this double-blind randomized outpatient clinical trial is to determine the pre-post change in the Flibanserin group and investigate the

extent to which Flibanserin normalizes brain activity in women with HSDD and the extent to which regional brain activation is associated with changes in symptoms and behavior (as measured with self-report measures of sexual desire and/or eye-tracking movements).

The study is registered on clinicaltrials.gov.

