***Data from Five 24-Week, Randomized, Double-Blind Placebo-Controlled Trials in Premenopausal Women with HSDD***

The data presented below are derived from five 24-week randomized, double-blind, placebo-controlled trials in premenopausal women with acquired, generalized HSDD. In these five trials, the frequency and quantity of alcohol use was not recorded. Three of these trials (Studies 1 through 3) also provided efficacy data [see **Clinical Studies**]. One of these trials (Study 5) did not evaluate the 100 mg bedtime dose.

In four trials, 100 mg ADDYI at bedtime was administered to 1543 premenopausal women with HSDD, of whom 1060 completed 24 weeks of treatment. The clinical trial population was generally healthy without significant comorbid medical conditions or concomitant medications. The age range was 18-56 years old with a mean age of 36 years old, and 88% were Caucasian and 9% were Black.

Serious adverse reactions were reported in 0.9% and 0.5% of ADDYI-treated patients and placebo-treated patients, respectively.

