### **Adverse Reactions Leading to Discontinuation**

The discontinuation rate due to adverse reactions was 13% among patients treated with 100 mg ADDYI at bedtime and 6% among patients treated with placebo. Table 1 displays the most common adverse reactions leading to discontinuation in four trials of premenopausal women with HSDD.

**Table 1: Adverse Reactions\* Leading to Discontinuation in Randomized, Double-blind, Placebo-controlled Trials in Premenopausal Women with HSDD**

	PLACEBO (N=1556)	ADDYI (N=1543)
Dizziness	0.1%	1.7%
Nausea	0.1%	1.2%
Insomnia	0.2%	1.1%
Somnolence	0.3%	1.1%
Anxiety	0.3%	1%

\*Adverse reactions leading to discontinuation of > 1% of patients receiving 100 mg ADDYI at bedtime and at a higher incidence than placebo-treated patients.

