### **Most Common Adverse Reactions**

Table 2 summarizes the most common adverse reactions reported in four trials of premenopausal women with HSDD. This table shows adverse reactions reported in at least 2% of patients treated with ADDYI and at a higher incidence than with placebo [see **WARNINGS AND PRECAUTIONS**]. The majority of these adverse reactions began within the first 14 days of treatment.

**Table 2: Common Adverse Reactions\* in Randomized, Double-blind, Placebo-controlled Trials in Premenopausal Women with HSDD**

	PLACEBO (N=1556)	ADDYI (N=1543)
Dizziness	2.2%	11.4%
Somnolence	2.9%	11.2%
Nausea	3.9%	10.4%
Fatigue	5.5%	9.2%
Insomnia	2.8%	4.9%
Dry mouth	1.0%	2.4%

\* Adverse reactions reported in ≥ 2% of patients receiving 100 mg ADDYI at bedtime and at a higher incidence than placebo-treated patients.

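### The closing safety clause compares related adverse events above mild with placebo but sets no counting unit, margin, test or interval, so 60 women per arm cannot give it a reliable answer

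*Combined protocol and SAP*

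**What the plan says.** The clause stands in Section 11, under Statistical Hypotheses, at the end of the electrophysiology item. The list it closes opens with "A significant and clinically meaningful change from baseline for each subject pre- and post-treatment with flibanserin is as follows". After a chain of effect-size conditions on desire, reaction time, EEG and eye movement, a separate sentence reads "There will be no adverse events of more than mild severity which are rated as possibly, probably, or definitely related to acute, oral administration" and continues "of flibanserin to a greater extent than PBO in HSDD participants".

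Other parts of the protocol bear on it:

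- **Arm size and exposure.** Section 5 assigns 60 women to flibanserin and the same number to "placebo (100 mg once daily at bedtime for 8 weeks, n = 60 subjects".
- **Known tolerability.** Section 12 reports "The discontinuation rate due to adverse reactions was 13% among patients treated with 100 mg ADDYI at bedtime and 6% among patients treated with placebo". Its Table 2 shows dizziness 11.4% v 2.2%, somnolence 11.2% v 2.9% and nausea 10.4% v 3.9%, and it adds that "The majority of these adverse reactions began within the first 14 days of treatment".
- **Source of those figures.** They come from 24-week trials in premenopausal women, where "The age range was 18-56 years old with a mean age of 36 years old". Half of this trial's women are to be postmenopausal, and the age limit is 74.
- **Data collected.** Section 28 records severity (mild, moderate, severe) and relationship to study drug for every adverse event.

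No other rule for comparing safety between arms appears in the readable text.

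**The concern.** The clause is worded as a comparison with placebo, but it lacks everything a comparison needs: a unit (women or events), an estimate, a tolerated excess, a test and an interval. The two readings a later analyst would most likely choose pull in opposite directions. A bare comparison of counts can declare an excess from chance alone. A significance test at this sample size will usually declare no excess even if the true rate is about double. Since the text does not choose, the choice could be made after the data are seen.

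The description of exposure also does not fit. Acute administration is not what Section 5 describes, so it is unclear which events fall inside the clause.

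At stake is the only stated between-arm safety conclusion, in a trial where half the women belong to the group for which the protocol says the drug is not approved.

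**Working it through.** **Plan's own figure.** There is none for this clause. The 95% power in Section 10 concerns the repeated-measures ANOVA and has no bearing here.

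**Inputs.** n = 60 per arm (Section 5). The documents give no rate of related events above mild, so a proxy is needed. The nearest figures are discontinuations for adverse reactions, 13% v 6% (Section 12). I also use half those rates (6.5% v 3%), and common rates down to 1%.

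**Reading A: raw count of women, tie passes.** Let X_F and X_P be independent Binomial(60, p). The clause fails when X_F > X_P. With identical arms, symmetry gives

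P(fail) = [1 − P(X_F = X_P)] / 2.

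| Common rate | P(tie) | P(fail) |
|---|---|---|
| 1% | 0.4195 | (1 − 0.4195)/2 = 0.290 |
| 3% | 0.2213 | (1 − 0.2213)/2 = 0.389 |
| 6% | 0.1554 | (1 − 0.1554)/2 = 0.422 |
| 13% | 0.1086 | (1 − 0.1086)/2 = 0.446 |

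The failure probability cannot reach 50% and is 46.4% at a common rate of 50%.

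With a true excess, P(X_F > X_P), summed exactly over both binomials, is 0.880 at 13% v 6% and 0.756 at 6.5% v 3%. At the serious-reaction rates in Section 12 (0.9% v 0.5%) it is 0.333.

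**Reading B: fails only if significantly more on flibanserin.** Fisher's exact test at 0.05, n = 60 per arm, summing the joint binomial probabilities of all tables that reject with flibanserin higher:

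| True rates | Two-sided | One-sided |
|---|---|---|
| 13% v 6% | 0.157 | 0.270 |
| 6.5% v 3% | 0.045 | 0.096 |
| 6% v 6% | 0.007 | 0.019 |
| 13% v 13% | 0.013 | 0.030 |

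At 13% v 6% the clause would therefore pass about 84% of the time (two-sided) or 73% (one-sided).

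**What an estimate would show.** If 13% v 6% were observed:

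- SE = √(0.13×0.87/60 + 0.06×0.94/60) = 0.0532.
- 95% CI = 0.07 ± 1.96×0.0532 = −0.034 to 0.174, or about −3 to +17 percentage points.

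**Postmenopausal women.** Assume an even split, so about 30 receive flibanserin (the readable text states no stratification). Zero events in 30 still allows a true rate up to 1 − 0.05^(1/30) = 0.095 (one-sided 95%).

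**Exposure wording.** Section 11 ties the events to acute dosing; Section 5 sets once-daily dosing for 8 weeks. The two do not describe the same exposure.

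**The case against.** The strongest reply is that the sentence is a prediction and not a decision rule. It follows the efficacy conditions as a separate sentence with no connective, under an introduction that speaks of each subject. No readable passage attaches a stop, a claim or a decision to it, and no adverse-event endpoint is listed in Section 4. That stands in part: how the clause joins the efficacy conditions is unclear, so it should not be called a formal criterion on which the trial succeeds or fails. But it is the only between-arm safety conclusion the plan states, and it still has to be evaluated somehow.

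A reader might infer three stronger things that the documents do not support:

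- **That the clause is defective because it would probably fail given the drug's known profile (88% at 13% v 6%).** If flibanserin truly causes more such events, failing is the right answer. The defects are failure with identical arms under one reading and low detection under the other.
- **That it contradicts the protocol's own data.** Table 2 is not restricted to related events above mild. A discontinuation can follow a mild event, and a moderate event need not lead to one. The source trials ran 24 weeks in premenopausal women and did not record how much alcohol was used, whereas this trial excludes women who report being unable to stop drinking. The figures make an excess likely; they do not rule the clause out. The early onset of most common reactions reduces the mismatch in duration but does not remove it.
- **That 42-45% false failure holds in general.** It needs the raw-count reading and a common rate of 6-13%. Under a one-sided Fisher test it is 2-3%.

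Safety collection is also not in question. All adverse events are recorded, side effects are asked about at weeks 1 and 2, and vital signs are taken at every visit.

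**Conclusion.** The concern holds as a fault in how safety would be concluded. The clause is undefined, and with 60 per arm neither reading is dependable. A count rule fails a drug identical to placebo 29% of the time at a 1% common rate, 39% at 3% and 42-45% at 6-13%. A significance rule misses 13% v 6% about 84% of the time two-sided, or 73% one-sided, and misses more at half those rates.

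The identical-arm figures rest on independent binomial counts of women, equal arms and ties counted as passes. The detection figures rest on the proxy rates. The missing unit, margin, test and interval, and the mismatch between acute and 8-week dosing, need no assumption. The primary EEG analysis is not affected.

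**What to change.** - Replace the clause with an estimate: the proportion of women with at least one treatment-emergent adverse event that is above mild and at least possibly related, over the 8-week treatment period. Report it by arm, with the flibanserin-minus-placebo difference and its 95% CI.
- Give the same table within premenopausal and postmenopausal women, labelled descriptive.
- Reconcile the reference to acute administration with Section 5, so that the exposure described matches the 8-week treatment period.
- State that the absence of a significant difference will not be read as comparable safety.

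The cost is a change of wording and one table built from severity and relatedness data that Section 28 already collects. No visit, sample size or treatment rule changes. The sponsor gives up a pass/fail safety statement. The intervals will be wide: about 21 percentage points across overall at the proxy rates (17.4 + 3.4 = 20.8), and wider within menopausal status.
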